### **2. Dissemination and Sustainability**

As discussed in **II.C.15.a**, ‘Complexity of Intervention’, our patient partners and other stakeholders are attracted to this study due to the simplicity of the PARTICS intervention and the likelihood that it will succeed. The approach is intuitive and relies on the patient-preferred pattern of use of reliever medication. This will help make the intervention sustainable. We have concrete buy-in from partners and stakeholders who are key to supporting the sustainability and implementation of our intervention based on our findings. Several companies have begun to discuss development of a single device SABA/ICS should our study be positive. By involving Teva, who has agreed to manage the drug delivery, we will de facto be able to demonstrate that the delivery is feasible, sustainable, and scalable across the United States. We are also designing our intervention to be easily scalable and sustainable on the patient side by solely using short (5 minute or less) YouTube-type videos that will be available on the internet for instructions and explanation of the intervention, which will be shown in the office when the patient is enrolled. It would subsequently be easy to use these in any practice adopting this approach. Post-study, physicians wishing to learn the NAEPP guidelines could access it for 20 minutes on the publicly available Asthma IQ site and receive CME credits and possibly maintenance of certification credits, further supporting sustainability on the provider-side. Our patient partners have agreed to help us present data in in their e-communities, and to their peers. Advocacy groups and professional society stakeholders have agreed to disseminate the results to their members and thus potentially create grass-roots demand. Our policy

stakeholders have received commitments to review these findings in their decision making bodies when the results have become available to classify the medications in the approach as the most reimbursable. The NAEPP has just determined that evaluation of the PARTICS approach will be among its top priorities for the next revision (Kiley 2015). We have indications from the prior chair of the last NAEPP that the study results would weigh heavily in consideration of the evidence based recommendations regarding PARTICS approaches.

We have included specific proposals from each of our stakeholders in the Dissemination Section. We will have each stakeholder group have a representative on a Dissemination Committee led by [name] who has extensive experience in implementation in primary care and family medicine practices. Some examples of how our stakeholders have already indicated their role in dissemination include:

1. Participating in our presentation at public forums and peer led blogs and social media;
2. Advocacy Groups – supporting grass roots campaigns for adoption of PARTICS;
3. Specialty Societies providing forums for provider and patient presentations using new formats including webinars, and online programs;
4. Insurers identifying pathways to get coverage for PARTICS medications, should the study be positive. See the Letters of Support, Organizational Support, for details. To consolidate and coordinate the plans for dissemination, we will devote part of our two-day meeting at the end of the study to review and plan dissemination.

Our structure reinforces the PCORI engagement principles:

**(a) Reciprocal Relationships:**

Reciprocal relationships are reflected in the use of stakeholders' insights and suggestions in the crafting of the study and this application as well as in ongoing study governance. The Executive Committee (EC) combines representatives from all stakeholder groups, not just the academic researchers to review and approve all major study decisions. The Operations Committee (OC) has assigned individuals to all stakeholder groups assuring participation and seeking feedback. Our initial attention to the recommendations of the stakeholders, as well as the initial face to face meeting, will further facilitate bidirectional communication and foster trust.

**(b) Co-learning:**

Co-learning has already occurred in the planning phases of this study. Each of the stakeholder groups has provided new insight and understanding incorporated into the development of PREPARE. The Vanguard cohort will provide another intense period of co-learning from the patients enrolled in this testing period as well as the stakeholders who will help assemble and interpret the feedback. The academic research team includes experts in interaction with each of our stakeholder groups with special emphasis on interaction and co-learning with the AA and H/L groups: [name], DNP; [name], MEd (AA asthma educator from the Caribbean); and co-investigator [name] [name] (allergist and native of Puerto Rico).

**(c) Partnership:**

All PREPARE stakeholders are equally valued partners. This is reflected in the structure of the EC, which includes representatives from patient and other stakeholder groups who will be a majority of the members of the EC. To ensure there are no barriers to communication, and thus

to partnership, interpreters and facilitators will be week available at all meetings. We have calibrated all stakeholder involvement to be respectful of the stakeholders' time. Finally, all members of all stakeholder groups will receive equal compensation (\$75/hr).

**(d) Trust, Transparency, Honesty:**

All stakeholders will participate in making major decisions and will have access to all study information beginning with representation of all groups on the EC. To date we have summarized and shared the comments from all stakeholders and highlighted back to the groups how this information has improved the study design including, for example, selection of outcomes, inclusion of the Vanguard cohort, and expansion of our Aims to include an important exploratory aim to better understand patient characteristics that may affect the success of the PARTICS strategy. Our stakeholders have continued to be willing to interact with the academic researchers and have been open in criticism as well as support for study design specifics. We believe this clearly demonstrates the great potential for ongoing trust and honesty in view of the transparency.

We have used the elements of the PRISM (Practical, Robust Implementation and Sustainability Model) as described by Feldstein et al (Feldstein, 2008) to evaluate and structure our dissemination and implementation model and to evaluate and promote sustainability. The model emphasizes 6 elements within an effective PRISM model (Intervention (Organizational and Patient Perspective), External Environment, Implementation and Sustainability Structure, and Recipients (Organizational and Patient)).

**3. Potential to improve healthcare and outcomes**

Our proposal is important to patients and to healthcare systems because it: 1) is based on strong preliminary data suggesting that the proposed approach will lead to sizeable improvements in outcomes important to patients **even when compared to enforced implementation of the NAEPP guidelines**; 2) addresses an important gap—the disproportionate asthma morbidity among affected minority populations (see **I.B.2**); 3) is strongly supported by patient and other relevant stakeholders; 4) is likely to be easy to disseminate; 5) will likely be sustainable because: a) it is intuitive for patients (treatment-preference concordance); b) it will be conducted with a real-life distribution system (Teva and electronic scripts in the EHR); and c) it is implemented with an easy, internet-accessible patient instruction system of **short** YouTube-like videos. We first review our preliminary data regarding PARTICS-type approaches, then review these other criteria of significance.

The proposal has *strong endorsement from all of our patient and other stakeholders*. Our patient partners have all indicated support of this approach to reduce asthma morbidity in a way that they feel would be helpful to them. This has been seconded by our advocacy stakeholders and our professional society stakeholders. Our health policy and insurance stakeholders have similarly indicated enthusiasm. As further evidence of buy-in, Teva has agreed to collaborate with us to implement the study, and agreed to donate drug, retail cost almost \$1 million.

**4. Patient-Centeredness**

**(a) Appropriate Engagement of Patients and Stakeholders**

We have already identified and engaged patients and stakeholders in study design and choice of outcomes (patients in our BELT study indicated they would like to experience fewer exacerbations). As discussed in those sections, patients and stakeholders will be active, important participants in choosing final study outcomes, study implementation, analysis, and dissemination. Patients and other stakeholders will serve on the trial's governing Executive Committee. Each member of the Operations Committee will serve as a liaison to each stakeholder group, ensuring bidirectional communication throughout the study timeline. We have engaged patient participation facilitators to assure continued engagement throughout the study. All stakeholders are valued for their contribution and are equally compensated.

**(b) Assuring Representativeness of the Population and the Data**

Our plans for assuring representativeness are described extensively in **II.C.15.c**, in addition to representative recruitment, we are reducing barriers to enrollment and participation by providing the option of enrolling patients at home visits and with opportunities for patients with low literacy via verbal consent and the option to do the monthly surveys via phone interview by trained staff.

**(c) Using Patient Reported Outcomes**

We use patient reported outcomes almost exclusively. Asthma task forces have identified them as critical outcomes. Our outcome, asthma exacerbations, is now used as THE major outcome for studies of new therapies in asthma. These outcomes are of interest to patients and focus on events or states of health that adversely affect patients' quality of life and ability to participate in usual activities, and result in loss of income or require financial expenditures. Our primary outcome, the rate of asthma exacerbations per year, is defined as the number of exacerbations, emergency room visits, or hospitalizations requiring oral or parenteral corticosteroids, per patient per year. It will be captured by subject self-report via a monthly asthma exacerbations questionnaire with follow up to the medical record or patient interview. All the study outcomes, their patient centeredness, and validation and properties are detailed in **section III**.

**(d) Supporting Dissemination**

PREPARE provides a strategy to help reduce excess asthma morbidity in AA and H/L populations. Our stakeholders are excited by this possibility. They have already indicated ways they will help to disseminate and implement this strategy by engaging with constituencies, insurance companies, distribution networks, and regulatory bodies to increase uptake and sustainability. Further, they will participate in a Dissemination Committee led by [name] to help assure dissemination success.

**5. Summary**

**(a) Vanguard:**

The Vanguard cohort of a subset of study participants will allow us to observe how well the protocol and materials work. This is a large, multi-centered, pragmatic trial, which implies

that the degree of investigator oversight is limited compared to traditional efficacy trials. The vanguard process attempts to compensate for limited oversight by testing appropriateness of our methods. The methods and issues we will test with the vanguard process include participant recruitment; the quality of our instructional videos and whether participants learn from them what we want them to learn; the accuracy of our eligibility questions to capture our population of interest; suitability of our consent form and registration process; capacity of our baseline intake and monthly surveys to capture variations in asthma control and exacerbations; randomization process; to assess the patients' understanding and acceptance of the PARTICS strategy; and finally allow us to better understand how our group of researchers will interact with our patient stakeholders and others through our Operations Committee and our Executive Committee. We will use data from the vanguard process to modify our methods and approach to conducting the full PREPARE study.

Full study difference: The Vanguard is testing process whereas the Full Study is testing the research question regarding PARTICS, explained below:

### **(b) Full Study**

The optimal strategy for ICS use for the management of persistent asthma remains unknown. Daily ICS use seems excessive to some patients when their asthma symptoms are controlled, and insufficient when they experience asthma exacerbations. In this PREPARE trial we will determine whether the PARTICS strategy--of using additional ICS concomitantly with rescue inhaler use--can reduce asthma exacerbations while allowing patients to adjust their ICS dose based on their perception of the intensity of their symptoms. We will do this in the setting of a pragmatic, patient-centered clinical trial which allows for greater generalizability and easier implementation of our results. While asthma is burdensome in terms of morbidity, mortality and costs, it is disproportionately so for the African American (AA) and Hispanic/Latino (H/L) communities. Conversely, these racial/ethnic groups constitute the minority of participants recruited in clinical trials.

PREPARE will address the need for pragmatic research to address the continuing burden of asthma in AA and H/L patients. In consultation with AA and H/L patients, health care providers, leaders of professional societies, advocacy groups, health policy leaders, pharmacists, and pharmaceutical manufacturers, results from PREPARE may demonstrate that implementing PARTICS may improve important asthma outcomes in these highly-impacted populations.

## **II. Study Design, Population, and Participant Recruitment**

### **A. Study Overview and Organization**

#### **1. Vanguard**

This is a randomized, open-label trial in AAs and H/Ls 18 years and older\* with asthma in which a standard of usual care, as requested by PCORI, is introduced (guided by the Asthma IQ educational program+ which we will call "provider educated care"), and then patients are randomized to addition of a PARTICS strategy vs. continuing this standard of provider-educated enhanced usual care. Underlying care will be standardized via provider certification in the educational component of the online Asthma IQ program. Self-identified+ AA and H/L patients at risk for exacerbations (e.g. on controller ICS with poor control, previous history of an exacerbation in previous 12 months or using ICS/LABA) will be identified from the clinical sites'

electronic health records and invited through their local provider's office\* to come for an enrollment visit.

The "Vanguard" cohort of 36 patients (16 AA and 20 H/L) from four sites represent our study sites' geographic, health system and practice size diversity; and patients that represent our anticipated enrollment of race, sex and age groups. Thirty two of the 36 (16 AA and 16 H/L) Vanguard patients will be English speaking patients enrolled 3:1 intervention (PARTICS) to non-intervention (enhanced usual care/Asthma IQ) so that we may observe how well the protocol and materials work. To test how the materials translated into Spanish work for the Spanish speaking patients, we will enroll 4 additional patients (total Vanguard patients 36) at one of the Vanguard sites that has a large Spanish speaking population (Mount Sinai). All 4 Spanish speaking patients will be placed in the intervention group to be able to sufficiently test the intervention materials. The intervention materials include everything included in the Usual Care group with additional materials. Each participant will be in the vanguard process for three months. After registration, vanguard participants will complete questionnaires at baseline (during registration) then two monthly questionnaires as the full study. In addition, the Vanguard cohort will be called at 1 week, 6 weeks and at 12 weeks to answer questions about the enrollment process, filling out the monthly questionnaires and the videos. The intervention group will be asked about the receiving the medication supplied by the study. The interviews will be audio recorded. This will enable transcription of the open-ended questions for the qualitative analysis. Those agreeing to attend the enrollment visit will have the study explained and complete informed consent facilitated by onsite study personnel or through video conferencing with central study staff. At the enrollment visit, entry criteria will be confirmed, consent obtained (potentially through a centralized 2-way video consent, baseline questionnaires completed, and the patient randomized (using a central randomization algorithm) to PARTICS with continuation of their provider-educated care or continued with their provider-educated care alone. Patients randomized to either study arm will watch a culturally appropriate video on proper inhaler technique followed by observation of the patient's inhaler technique. All enrollees will also receive instructions on completion of monthly questionnaires and general questions will be answered via the video communications or by local staff as necessary. Each enrollee will select one of the patient-partner designed inhaler pouches and clip\* to hold their quick relief inhaler(s). Those randomized to PARTICS will also view a patient partner-approved culturally appropriate video\* that explains how and why to use the PARTICS dual quick relief medications (ICS+SABA). Patient questions regarding PARTICS will be answered in real time via video communication. At the close of the visit, PARTICS patients will receive or be mailed an ICS inhaler with a counter and a Velcro band\* (used to attach the rescue ICS inhaler to the patient's current SABA (ICS study drug donated by Teva. For PARTICS ICS refills, patients will call the 800 number printed on the Velcro band when their counter reaches 40. Teva will send a new ICS inhaler directly to the address designated by the patient.

All patients (both PARTICS and control groups) will be asked to complete monthly questionnaires using validated instruments to assess exacerbations, symptoms, medical visits primarily driven by asthma (visits, ED visits, and hospitalization) and medication use. At enrollment patients will choose how they wish to receive reminders as well as—primarily complete the questionnaire (online, smart phone, mailed—exactly same questions and multiple choice answers for each method). Patients will be allowed to change methods whenever requested. Several of the instruments have been validated to be comparable across these response methods (Schatz 2007a, Schatz 2007b, and Schatz 2007c).

Before sites begin enrolling patients the study team will host centralized training for the site PI and key practice personnel, and all clinic team members will be instructed about the overall study protocol and the PARTICS approach.

## **2. Full study**

### **B. Full study differences:**

The Full study will enroll up to 1210 patients and will be conducted in up to 20 diverse health care settings across the country, the patients will be enrolled 1:1 intervention (PARTICS) to non-intervention. There will be one follow up call within the first month of enrollment to ask questions about the patients experience filling out the survey. There will be NO follow up calls to the patients at week 1, 6 and 12 to answer questions about the enrollment process, filling out questionnaires and the informational and instructional videos or questions to the intervention group about the medication supplied by the study. The patients will have one in person visit to enroll in the study then will receive monthly questionnaires for 12 to 15 months depending on when they are enrolled. Patients may also be given the option to enroll during a home visit. Home enrollment visits will include the same methods as on-site enrollment visits.

Those agreeing to enroll will have the study explained and complete informed consent facilitated by study personnel. At the enrollment visit, entry criteria will be confirmed, consent obtained, baseline questionnaires completed, and the patient randomized (using a central randomization algorithm) to PARTICS with continuation of their provider-educated care or continued with their provider-educated care alone. Patients randomized to either study arm will watch a culturally appropriate video on proper inhaler technique followed by observation of the patient's inhaler technique. All enrollees will also receive instructions on completion of monthly questionnaires and general questions will be answered staff as necessary. Each enrollee will select one of the patient-partner designed inhaler pouches and clip\* to hold their quick relief inhaler(s).

During the study visit, we will ask participants to exhale into a machine that determines nitric oxide gas levels in their breath. This procedure was not conducted in the Vanguard phase, and will only be conducted during the full study. In addition, patients will be asked if they agree to have 3 mL's of blood drawn for a complete blood count (CBC) with differential. The CBC results will include eosinophil counts that are associated with patients' response to inhaled corticosteroids. Depending on the site, the patients will either have their blood drawn during their enrollment or be sent to a contracted laboratory in the area. Samples will be processed either at the facility where the enrollment takes place, or by a contracted diagnostics company such as LabCorp.

Those randomized to PARTICS will also view a patient partner-approved culturally appropriate video\* that explains how and why to use the PARTICS dual quick relief medications (ICS+SABA). At the close of the visit, PARTICS patients will receive or be mailed an ICS inhaler with a counter and a Velcro band\* (used to attach the rescue ICS inhaler to the patient's current SABA (ICS study drug donated by Teva. In addition, patients randomized to PARTICS who answer "yes" to using a nebulizer on the intake questionnaire will receive a second ICS and an extra pouch to hold the ICS along with a Velcro strap to attach the additional pouch with the ICS to the nebulizer. For PARTICS ICS refills, patients will call the 1-800 number printed on the

Velcro band when their counter reaches 20. Teva will send a new ICS inhaler directly to the address designated by the patient. All patients (both PARTICS and control groups) will receive a refrigerator magnet with adherence instructions.

All patients (both PARTICS and control groups) will be asked to complete monthly questionnaires using validated instruments to assess exacerbations, symptoms, medical visits primarily driven by asthma (visits, ED visits, and hospitalization) and medication use. At enrollment, patients will choose how they wish to primarily complete the questionnaire (online, smart phone, mailed—exactly same questions and multiple-choice answers for each method). Monthly reminders to complete each monthly survey will be sent to patients through all methods of communication that the patient provides (text, email, phone call). Patients will be allowed to change methods whenever requested. Several of the instruments have been validated to be comparable across these response methods (Schatz 2007a, Schatz 2007b, and Schatz 2007c). In addition to monthly survey reminders, patients will also receive quarterly reminder text messages about the study and monthly surveys. Patients may opt out of the text messages at any time.

Before sites begin enrolling patients, the study team will host centralized training for the site PI and key practice personnel, and all clinic team members will be instructed about the overall study protocol and the PARTICS approach.

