#### **6. Blood draw (Eosinophils):**

During the enrollment visit, we will ask each participant if s/he agrees to have blood drawn.

The blood draw is to determine Eosinophil counts which are known to be associated with response to Inhaled Corticosteroids. The test used will be a complete blood count with differential (CBC with differential). The amount of blood needed for this test is 3 mL, collected in a purple top tube. This will be the only blood draw for the participant throughout the study. This procedure will only be conducted during the full study.

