## 5. Blood draw/Eosinophils

Peripheral blood eosinophils may identify asthmatics that are most responsive to Patient Activated Reliever-Triggered Inhaled CorticoSteroid (PARTICS). Eosinophil counts can be calculated by a complete blood count with differential. We will determine whether peripheral blood eosinophil count serves as an effect modifier of the relationship between treatment (PARTICS vs. usual care) and the study's primary outcome (number of asthma exacerbations per year). We will stratify participants based on a pre-specified peripheral blood eosinophil count threshold of 300/uL. This threshold is based on a frequently-used cutoff for 'eosinophil-high' status in the anti-eosinophil therapy literature (Giannetti 2016).

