## 6. Subgroup Analysis

Subgroup analyses for the primary efficacy outcome will be performed on the ITT population in order to explore whether the treatment effect is consistent across subgroups. Our goal is to determine the impact of PARTICS on asthma exacerbations in two pre-specified main subgroups determined by 1) race/ethnic group (African American vs. Hispanic/Latino) and 2) smoking status [i.e., participants who are previous (>10 pack- years)/current (or within 1 year) smokers vs. those who have not smoked (in the past year and <10py)] 3) patients with high FeNO vs. low and 4) patients with high eosinophil counts vs. low. Based on our prior experience, about 50% of our population will be smokers or ex- smokers.

Subgroup analyses to evaluate variation in treatment effect will be performed on the basis of tests for interaction using the same Andersen-Gill version of the Cox proportional hazards model as used in the primary analysis. The model will be including terms for treatment arm, subgroup, and treatment by sub-group interaction and adjust for all variables included in the primary model. Additionally, treatment effects within each categorical subgroup will be examined separately using analogous Andersen-Gill model. Event rates by treatment arm and hazard ratios with 95% confidence intervals will be reported for each subgroup. Forest plots will be generated displaying the estimated hazard ratios and 95% confidence intervals for each subgroup will be presented. Variation in treatment effect will be assessed on the basis of tests for interaction in the Andersen-Gill version of the Cox proportional hazards model described above. Treatment effects estimated within each categorical subgroup will be considered exploratory/hypothesis generating. Thus, no adjustment for multiple testing will be employed.

Additional exploratory subgroup analyses will be performed investigating the effect of the following factors: 1) modality in which questionnaires have been returned; 2) patients' attitude towards ICS from the validated BMQ (skeptical (low necessity, high concerns), indifferent (low necessity, low concerns), ambivalent (high necessity, high concerns), accepting (high necessity, low concerns)); 3) presence of depressive symptoms (yes/no); 4) health literacy status (low or marginal versus high); and 5) patient adherence barriers from the validated ASK12 questions 1,2,3 and 11 related to measures of inconvenience, forgetting and

cost.

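### The single eosinophil sample has no required order relative to open-label randomisation or first study ICS, and the sections on its timing disagree, so the eosinophil subgroup can rest on a post-allocation value

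*Combined protocol and SAP*

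**What the plan says.** Under Full study differences (section II), "The patients will have one in person visit to enroll in the study". Within that visit entry criteria and consent come first, then "baseline questionnaires completed, and the patient randomized (using a central randomization algorithm) to PARTICS" or usual care. The blood draw is not listed as a step before randomisation. The same section continues: "At the close of the visit, PARTICS patients will receive or be mailed an ICS inhaler with a counter and a Velcro band". On the sample, it says that, depending on the site, "the patients will either have their blood drawn during their enrollment or be sent to a contracted laboratory in the area". Blinding/medications (II.C.5) makes the trial open label.

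Blood draw (Eosinophils) (II.D.6) makes the sample voluntary: "During the enrollment visit, we will ask each participant if s/he agrees to have blood drawn". It adds that no other blood is taken during the study, so there is no second sample to fall back on.

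The count is then used as an effect modifier. Blood draw/Eosinophils (III.C.5) states: "We will stratify participants based on a pre-specified peripheral blood eosinophil count threshold of 300/uL". Subgroup Analysis (III.E.6) lists "patients with high eosinophil counts vs. low" among the main subgroups. It tests treatment-by-subgroup interaction in the Andersen-Gill model and reports a hazard ratio for each subgroup.

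Three passages in section VII give a different timing. Sources of Materials (VII.A.2) puts the specimen at enrolment, Procedural Risks (VII.B.4) puts it during the study visit, and Blood Draw Risks (VII.B.5) puts it during enrolment. None mentions the outside laboratory or states an order relative to randomisation.

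**The concern.** A subgroup comparison is protected by randomisation only if the variable that defines the subgroup cannot be affected by allocation. That protection can fail here in two ways.

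First, the value. A PARTICS patient sent to a laboratory after the visit may already be using the study ICS. The plan's FeNO outcome section (III.C.4) says corticosteroids target Type 2 (eosinophilic) inflammation, and the subgroup section ties blood eosinophils to it. If added ICS lowers the count, some patients just above 300/uL move into the low group in one arm only.

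Second, whether a value exists. The draw is optional. If the patient must go elsewhere after learning the arm, attendance may differ by arm. This does not depend on any effect of ICS on the count.

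At stake are the within-subgroup hazard ratios and, to a lesser extent, the answer on effect modification. Readers could use either to decide which patients suit the strategy.

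**Working it through.** **1. Sequence.** Side by side, the sections allow three orders: a draw before the arm is revealed, a draw later in the same visit, and a draw at a laboratory afterwards. No section sets a window, requires one of these orders, or keeps late samples out of the subgroup. Section VII is compatible with the first two orders only, so it conflicts with the laboratory route unless that visit counts as part of enrolment.

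**2. The plan's nearest figure.** No figure covers this point. Sample Size (III.E.8) gives 80% power for a 32% reduction with 300 per arm. Inputs: 0.4 events per year in control, 15 months, 31.25% uniform loss.
- Mean exposure = 1.25 x (1 - 0.3125/2) = 1.055 years.
- Events: 300 x 0.4 x 1.055 = about 126.6 in control; times 0.68 = about 86.1 in PARTICS.
- SE of log HR = sqrt(1/126.6 + 1/86.1) = 0.140.
- Power = Phi(0.386/0.140 - 1.96) = about 79%, which agrees with the stated 80%.
- SE of the contrast between two such subgroups = 0.140 x sqrt(2) = about 0.20.

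**3. Size of relabelling, on assumed inputs.** The documents give none of these: log-normal counts X with median 200 or 250/uL and log-SD 0.7; event rate proportional to X^0.3; a fraction f of PARTICS draws made after study ICS; a proportional fall d in those counts.
- Share above a cut c: 1 - Phi(ln(c/median)/0.7).
- Share of events above c: 1 - Phi((ln(c/median) - 0.3 x 0.49)/0.7).
- A late draw acts like a cut of 300/(1 - d).

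Worked case (median 250, f = 0.5, d = 0.30; effective cut 300/0.7 = 428.6):
- High share: control 0.397; late draws 0.221; PARTICS overall 0.309. So 0.088/0.397 = 22% of truly high PARTICS patients are relabelled.
- Event share in high: control 0.480; late draws 0.288; PARTICS overall 0.384.
- Constant HR 0.80. High: 0.80 x (0.384/0.309)/(0.480/0.397) = 0.823. Low: 0.80 x (0.616/0.691)/(0.520/0.603) = 0.827. Ratio of the two = 0.995.
- Benefit in high only (HR 0.68 v 1.00). High: 0.68 x 1.028 = 0.699. Low: [(0.520 + 0.68 x 0.096)/0.691]/(0.520/0.603) = 0.982. Ratio = 0.71, against a true 0.68.

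| Assumption | Truly high relabelled | Subgroup HRs (true 0.80) | High/low ratio, constant effect (true 1.00) | High/low ratio, benefit in high only (true 0.68) |
|---|---|---|---|---|
| f 25-50%, d 15-30% | 5-25% | 0.81-0.83 | 0.995-1.003 | 0.69-0.71 |
| all draws late, d 15-30% | 22-51% | 0.82-0.87 | 1.01-1.03 | 0.71-0.76 |
| ICS does not move the count | 0% | 0.80 | 1.00 | 0.68 |

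The worked shift from 0.68 to 0.71 is about 0.045 on the log scale, roughly a quarter of the 0.20 SE in step 2.

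**4. No treatment effect.** With 10-50% late draws, a 10-30% fall and an event rate 1.5 to 2 times higher in the high group, about 3 to 53 of 600 PARTICS patients are relabelled. Subgroup rate ratios move from 1.00 to at most about 1.06 (high) and 1.07 (low).

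Arm-dependent attendance cannot be sized from the documents.

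**The case against.** Section VII says three times that blood is taken at enrolment or during the visit, and the laboratory sentence states no sequence. A reader might infer that every referral-site sample follows randomisation and study ICS. The documents do not say so: a same-day draw, or one before the arm is revealed, fits the text. Some inhalers are mailed and use depends on symptoms, so prior exposure is uncertain. The plan applies the word baseline to FeNO, not to this count. This stands, and it makes the defect an unreconciled gap rather than a planned post-treatment measurement.

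All participants are already prescribed daily ICS, and nothing in the plan shows that added as-needed ICS lowers blood eosinophils in such patients within the delay involved. This also stands; without such an effect, relabelling bias is nil. Arm-dependent attendance remains possible.

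A reader might also infer that the interaction test is biased. Under a constant effect both subgroup hazard ratios drift together and their ratio hardly moves. Only if benefit is confined to high-count patients is it attenuated, and then slightly at the assumed late fractions.

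Finally, III.E.6 labels within-subgroup effects exploratory. That limits the weight of the problem, but those hazard ratios will still be reported, and the repair is cheap.

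**Conclusion.** The point holds as a gap in the plan with modest consequences. The timing passages contradict each other, and as written the count that defines the eosinophil subgroup can be measured, or be absent, after allocation is known. Within-stratum comparisons may then no longer be fully randomised.

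The size cannot be derived, because the number of referral draws, the delay and the effect of added ICS on the count are not stated. On the assumed ranges the distortion of the subgroup hazard ratios is a few hundredths, and the interaction is affected less. Nothing here supports a claim that the main result is at risk: eosinophils are not a covariate in the primary model (III.E.4), and the ITT comparison is unaffected.

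**What to change.** - Reconcile Full study differences and II.D.6 with VII.A.2, VII.B.4 and VII.B.5, so that one statement governs where and when the sample is taken.
- Where blood is drawn on site, draw it before the arm is revealed. A rule of 'on the day of randomisation' is not enough, because it admits draws made after the reveal.
- Record the date and time of the draw relative to randomisation and to receipt or first use of the study inhaler.
- In III.C.5 and III.E.6, pre-specify the eosinophil interaction restricted to draws made before the arm was revealed, alongside the analysis of all draws. Referral-site draws made after the reveal but before inhaler receipt can be added as a separately flagged set. Usual-care patients have no receipt date, and attendance may already depend on the arm, so this set should not be merged silently.
- Report late and absent draws by arm.

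The cost is protocol and SAP wording, one date/time field, and a smaller, less precise restricted analysis, possibly much smaller if many draws were late. That is why the all-draws analysis should stay rather than setting every late count to missing. Follow-up Intensity (II.C.7) and Figure 3 put the end of enrolment at 30 April 2020. For patients already enrolled, only the analysis and reporting parts can apply, and only where draw dates can be recovered.
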